4. SELECTION OF STUDY POPULATION

4.1. Study population

465 patients with functional bowel disorders with abdominal pain and bloating/flatulence from 18 to 75 years old will be randomized into the study. 665 patients will be screened (approximately 30% screen failure rate).

Patients will be randomized into three groups at the ration 1:1:1 (155 in every group):

- Mebeverine + Simethicone, film coated tablets, 135 mg + 80 mg, one tablets 3 times a day during 4 weeks;
- Duspatalin[®] film coated tablets, 135 mg, one tablets 3 times a day during 4 weeks;
- Espumisan® capsules 40 mg, 2 capsules 3 times a day during 4 weeks.

4.2. Inclusion criteria

Patients should corresponds to all inclusion criteria listed below:

- 1. Signed Informed Consent Form;
- 2. Males and females aged 18 to 75 years old (inclusive);
- 3. Abdominal pain and bloating/flatulence due to functional bowel disorder (including IBS, chronic functional constipation, chronic functional diarrhea or functional abdominal bloating);
- 4. Episodes of abdominal pain for at least 3 months, with a frequency of at least 3 times a month:
- 5. Abdominal pain intensity of 4 to 9 points (inclusive) when assessed on the NRS-11 scale (i.e. weekly average, with daily recording of the worst pain for the last 24 hours during last week of Screening and Run-in period);
- 6. Bloating/flatulence intensity of of 4 to 9 points (inclusive) when assessed on the NRS-11 scale (i.e. weekly average, with daily recording of the worst bloating episode for the last 24 hours during last week of Screening and Run-in period);
- 7. Patients' consent to use adequate contraception methods throughout the study. Adequate contraception methods include:
 - a. oral contraceptives or contraceptive patches,
 - b. condom or diaphragm (barrier method) with spermicide, or
 - c. an intrauterine device

4.3. Exclusion criteria

Patients will be not eligible for participation in this study if he/she will meet at least one of the criteria described below:

- 1. Hypersensitivity to mebeverine, simethicone, drotaverin, excipients of the studied products, or contraindications;
- 2. Intake of tricyclic antidepressants, eluxadoline, linaclotide, selective serotonin re-uptake inhibitors, rifaximin, lubriprostone within the last week before screening;
- 3. New prescription or any change in probiotic drug therapy (including change in the drug or dosage regimen) during the last month before screening;
- 4. History of intestinal obstruction, stricture, toxic megacolon, GI (gastro-intestinal)

Confidential Page 47 of 94

- perforation, fecal impaction, gastric banding, bariatric surgery, adhesions, ischemic colitis, or impaired intestinal circulation (e.g. aorto-iliac disease);
- 5. History of major gastric, hepatic, pancreatic or intestinal surgery (appendectomy, hemorrhoidectomy, or polypectomy allowed as long as occurred > 3 months prior to trial screening; uncomplicated laparoscopic or open cholecystectomy is allowed if no history of post-operative biliary tract pain and surgery occurred > 3 months prior to screening);
- 6. Significant and progressive enlargement of the liver, spleen, lymph nodes; ascites; palpable tumor formation in the abdominal cavity / pelvis according to physical examination, hepatic cirrhosis;
- 7. Significant concomitant acute or chronic disease (cardiovascular, gastrointestinal, endocrine, immunological, metabolic, bronchopulmonary, urinary system) or any condition that, according to Investigator, is a contraindication for the patient to participate in the study if interference with the study performance;
- 8. Any inflammatory bowel disease (Crohn's disease, ulcerative colitis, any infection including bacterial, viral, protozoa, helminthosis);
- 9. Elevated fecal calprotectin level 1 month before or at screening which indicates the presence of inflammatory GIT disease;
- 10. Unexplained GI bleeding within 3 months prior to screening;
- 11. Confirmed diagnosis of bile acids malabsorption;
- 12. History of any malignant disease except basal cell carcinoma of skin and vesical cervix carcinoma in situ which were cured ≥ 5 years ago;
- 13. Confirmed diagnosis of celiac disease;
- 14. Confirmed hereditary galactose or fructose intolerance, total lactase deficiency, sucrase-isomaltose insufficiency, glucose-galactose malabsorption syndrome;
- 15. Diet changes (e.g, switching to fermented foods, a gluten-free diet) within the 1 months prior to screening;
- 16. Planned elective surgery during the study;
- 17. Pancreatic exocrine insufficiency or acute pancreatitis;
- 18. Endometriosis in women;
- 19. Positive results of tests for HIV, hepatitis B or C, at the moment of screening;
- 20. Drugs or alcohol abuse at screening or in the past, which, in the Investigator's opinion, makes the patient not eligible for participation in the study;
- 21. Participation in another clinical study or another study drug administration within 30 days prior to screening;
- 22. Pregnant or lactating women, or women planning to get pregnant during the clinical study; women of child-bearing potential (including those without history of surgical sterilization and women with <2 years post-menopause) not using adequate contraception methods;
- 23. Inability to read or right; unwillingness to understand and comply with Protocol procedures; non-compliance with medication dosing regimen or procedures which, in the Investigator's opinion, may affect study results or the patient's safety and prevent the patient's participation in the study; any other concomitant diseases or severe mental disorders, which make the patient ineligible for study participation, limit the legal basis for Informed Consent procedure, or may affect the patient's ability to participate in the study.

Confidential Page 48 of 94

4.4. Exclusion of patients from the study after randomization

The patient can withdraw the consent any time without any explanations. In the event of significant deviations, which, according to the Investigator, could impede the patient's participation in the study or interpretation of effectiveness or safety parameters, the patient should be excluded from the study. Criteria for early exclusion of patients from the study are provided in section 6.14

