3.3. Study treatment period

3.3.1. Visit 2, Randomization (Week 0, Day 1)

On Visit 2 (Week 0, Day 1) patients who meets all inclusion/exclusion criteria, will be randomized into one of the three groups at a 1:1:1 ratio. Vital signs, body weight, AEs and concomitant medication will be evaluated. Patients will assess their quality of life by completing IBSQOL.

Group	Study product	Number of patients	
1	Mebeverine+Simethicone, 135 mg+80 mg, three times a day	155	
2	Duspatalin® 135 mg three times a day	155	
3	Espumisan®, 80 mg (2 capsules 40 mg) three times a day	155	

Confidential Page 28 of 94

The study will be open, with no treatment blinding.

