6.14. Subject Withdrawal from the Study

All subjects are free to withdraw from participation in this study at any time, for any reason, specified or unspecified, and without penalty or loss of benefits to which the subject is otherwise entitled.

The Study Termination form must be completed for all subjects who did not fail screening.

In case of premature termination of the subject from the study, the primary reason for this premature termination is to be indicated according to the following definitions:

- Adverse event: discontinuation due to any adverse event (AE) with a corresponding entry reflected on the Adverse Events form in the eCRF
- Lack of efficacy: subject fails to respond to the study drug at an acceptable level where the subject or the Investigator feels it is in the best interests of the subject to seek another treatment.
- Lost to follow-up: the subject fails to return to the study site for scheduled visits and does not respond to telephone or written attempts to contact.
- Withdrew consent: subject decides to stop his/her participation in the study for any reason other than an AE, or is unable to complete the study as described in the clinical study protocol (e.g., subject is relocating to another location).
- Administrative: the Sponsor decides to discontinue the study (either at the study site or the entire study), e.g., general safety problems leading the Sponsor to entirely stop the study.
- Protocol violation anything which is in direct violation of the clinical study protocol (e.g., inclusion/exclusion violation)

If possible, the Investigator must first discuss the discontinuation with the Medical Monitor. Otherwise, the Investigator should discuss the issue of discontinuation with the Medical Monitor within 24 hours after discontinuation.

The reason for the patient's discontinuation should be specified in the source documentation and on the electronic Case Report Form. If the patient discontinues participating in the study for more than one reason, the main reason should be given. Occurrence of an AE or SAE should be specified as the reason for the withdrawal of the patient's consent due to such AE or SAE.

Confidential Page 63 of 94

In addition, the Sponsor shall be entitled to terminate the study at any time. The Investigator is entitled to terminate the study at any time for medical or regulatory reasons. Termination of the study should be done after mutual consultations between the Investigator and the Sponsor only.

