7.5. Early discontinuation visit

In case of early termination of participation, after Visit 2 (Week 0, Day 1) and before Visit 3 (Week 4, Day 29), the patient should be invited to the study site to undergo an early discontinuation Visit (ED) assessments. The Investigator should make every effort to conduct ED

ED Visit should include all procedures of Visit 3 (Week 4, Day 29). If ED Visit cannot be carried out in full, the Investigator should coordinate their actions with the Medical Monitor. On ED Visit the patient should return all used and unused packages of the study drug. The patient will be given recommendations for further treatment as part of standard therapy.

If possible, the Investigator should discuss the patient's early discontinuation from the study with the Medical Monitor in advance. Otherwise, the Investigator should contact the Medical Monitor within 24 hours after the early discontinuation of the patient

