9.7.2. Primary end points analysis

The FAS will be the main sample for efficacy assessment in this study performed to confirm superiority. Additional analysis of the primary efficacy endpoint will be performed in the per protocol (PP) set.

For the difference of changes in sum scores of NRS-11 pain and bloating/flatulence intensities after 4 weeks of treatment versus baseline between the groups Mebeverine+Simethicone versus Duspatalin® and Mebeverine+Simethicone versus Espumisan®, a two-sided 95% confidence interval (CI) will be constructed, which is equivalent to a 97.5% one-sided CI. The confidence interval will be constructed using ANCOVA, which will include treatment and site as fixed effect, and baseline parameter will be included in the model as covariate. To test the hypothesis of superiority of the FDC Mebeverine+Simethicone versus every comparator (Duspatalin® and Espumisan®), the upper confidence limit will be used. The null hypothesis (H₀: no difference in change from baseline of sum of bloating/flatulence and pain scores between the FDC and corresponding comparator, will be rejected in favor of the alternative hypothesis (H_a: larger change from baseline of sum of bloating/flatulence and pain scores in the fixed-dose combination Mebeverine+Simethicone group) only if the upper limit of two-sided 95% CI does not contain the value 0. In addition the study will be considered successful in case both superiority hypothesizes are proven, i. e. upper limit of two-sided 95% CI does not contain the value 0 for both constructed confidence intervals. In this case, the conclusion will be drawn on the fixed-dose combination of Mebeverine+Simethicone to be superior versus Duspatalin® (mebeverin) and Espumisan® (simethicone) for the decrease of both pain and bloating/flatulence intensity.

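### Protocol 4.4 lets an unblinded investigator's judgement about a deviation end a randomised patient's follow-up, so the timing of that decision sets which week's score is analysed

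*Protocol*

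**What the plan says.** Protocol 4.4 deals with patients who are already randomised. Its trigger is a judgement: "In the event of significant deviations, which, according to the Investigator, could impede the patient's participation in the study". A second ground, together with the instruction itself, then follows: "interpretation of effectiveness or safety parameters, the patient should be excluded from the study". The consequence is leaving the study, not only stopping study drug or leaving the per-protocol (PP) set. For criteria, 4.4 points to 6.14. That section lists the reasons to be recorded at premature termination, one of them being "anything which is in direct violation of the clinical study protocol", and it sets no threshold.

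Protocol 3.3.1 states "The study will be open, with no treatment blinding". On oversight, 6.14 says "If possible, the Investigator must first discuss the discontinuation with the Medical Monitor"; failing that, the discussion takes place within 24 hours afterwards.

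Protocol 7.5 gives a patient who leaves early one visit with the Visit 3 procedures, at which study drug is returned and advice on standard therapy is given. Neither 6.8, 6.14 nor 7.5 asks for diary entries after that visit.

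For the analysis, Protocol 9.7.2 says "The FAS will be the main sample for efficacy assessment in this study performed to confirm superiority". SAP 4.2.1 and 4.2.2 define Week 4 as Days 23-29 when treatment lasted 28 days, and otherwise as the last 7 days up to the last treatment day. Protocol 9.9 adds last observation carried forward. Significant protocol violations already have a place in the plan: they lead to exclusion from the PP set (Protocol 9.4), decided at the Blind Data Review (SAP 4.1).

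**The concern.** The primary question is the change after 4 weeks in the full analysis set (FAS), whose purpose is to keep patients who deviate. Section 4.4 asks someone who knows the arm to decide, during treatment, whether a deviation harms the interpretation of efficacy, and to take the patient out of the study if it does.

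Such a decision can depend on both arm and response. For example, Protocol 5.8 prohibits other products for intestinal pain and bloating, and a patient with poor relief has the most reason to take one. Patients and investigators also know which component a monotherapy arm lacks.

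The judgement resembles the one that the plan reserves for PP exclusions at the Blind Data Review. Under 4.4 it is made earlier and with the arm known, and the calendar Week 4 scores cannot be recovered afterwards. At stake is a selection effect in the main superiority analysis that a larger sample would not remove.

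**Working it through.** **The plan's own figures.** Inputs from Protocol 9.2: difference 1.0, SD 2.5, two-sided alpha 0.05, power 90%, drop-out 15%.

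- Per group: n = 2 × [2.5 × (1.960 + 1.282) / 1.0]² = 131.3, rounded up to 132. This agrees with the plan.
- With drop-out: 132 / 0.85 = 155.3, against a stated figure of about 155.
- Power for both comparisons, with correlation 0.5 from the shared combination arm: 83.5%, against a stated figure of about 80%.

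These figures are not in dispute. The allowance leaves 155 × 0.85 = 131.75 evaluable patients per arm. It protects precision but not against removals that depend on arm.

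**What happens to a removed patient.**

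1. The investigator applies 4.4 at some day before Day 29.
2. The early discontinuation visit collects the diary to that point (7.5).
3. With at least one efficacy assessment after baseline, the patient remains in the FAS (Protocol 9.4, SAP 4.1).
4. SAP 4.2.1 fills Week 4 from the last 7 treatment days.
5. The Day 23-29 scores do not exist, so the day chosen in step 1 determines the value analysed in step 4.

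That the diary stops is an inference from steps 1 and 2 and from the absence of any provision for later entries. The documents do not state it in words.

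**Size.** Let k be the net extra removals in one arm of 155, and s the number of points by which the recorded value is better than the unobserved Week 4 value. Removed patients stay in the mean, so

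shift in the contrast = k × s / 155.

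The standard error of the contrast with 155 per arm is 2.5 × √(2/155) = 0.284. With no true difference, the one-sided error of one comparison is 1 − Φ(1.960 − shift/0.284), which is 2.5% at zero shift. Both k and s are assumptions, and the table takes the direction that favours the combination.

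| k (share of 155) | s | Shift (points) | One-sided error |
|---|---|---|---|
| 2 (1.3%) | 1 | 0.01 | 2.8% |
| 2 | 2 | 0.03 | 3.1% |
| 8 (5.2%) | 1 | 0.05 | 3.8% |
| 8 | 2 | 0.10 | 5.5% |
| 8 | 4 | 0.21 | 10.9% |
| 16 (10.3%) | 1 | 0.10 | 5.5% |
| 16 | 2 | 0.21 | 10.9% |

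With the sign reversed, the same shifts count against the combination. If the extra removals are in the combination arm, both contrasts move the same way, so the requirement to win both comparisons does not cancel the effect.

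**The case against.** Several points on the other side stand.

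- **The SAP gives early stoppers a value.** A reader of 4.4 might infer that removed patients drop out of the primary analysis. For k patients each D points worse than their arm mean, that would shift the mean by k × D / (155 − k); with k = 8 and D = 3 this is 24 / 147 = 0.16. The documents do not support that reading, because the last-7-treatment-days rule keeps these patients in the FAS mean. The problem is substitution of an earlier week, not absence.
- **Section 6.14 does not order removal.** A reader might take it to mean that any violation ends participation. It lists reasons to be recorded once a patient has terminated, and the trigger in 4.4 is limited to significant deviations.
- **The decision is not unchecked.** The Medical Monitor is consulted. That is a real restraint, but the consultation is not masked and need not come first.
- **The 15% drop-out is not the number at risk.** It covers every cause in 6.14, including adverse events, lack of efficacy, loss to follow-up and withdrawn consent. Nothing in the documents says how many patients 4.4 would remove.
- **Opportunity is limited.** The Day 15 call is the only scheduled contact between Day 1 and Day 29, and Protocol 7.2.2 lists no review of scores there. The diary is returned and compliance calculated at Visit 3, so a deviation first found then costs no Week 4 data. The call does cover concomitant medication, and unscheduled visits are possible, so earlier detection is not ruled out.
- **An on-treatment value is a legitimate choice.** Scores recorded after a patient moves to standard therapy answer a different question. This argues against imposing them as the primary value, but not against collecting them.

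**Conclusion.** The point holds as a weakness that is cheap to correct. In an open-label trial with a patient-reported endpoint, a subjective removal made with the arm known decides which week's score enters the main analysis, and the true Week 4 score is then never available as a check.

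Neither the size nor the direction of any bias can be determined from the documents. At k = 8 with s of 1 to 2 points, the shift is about 0.05 to 0.10 points against the planned 1.0. This rests on assumed k and s, on a net imbalance between arms (similar removals in each arm would largely cancel), and on 155 analysed per arm with SD 2.5. The larger entries in the table only show the range; nothing in the plan suggests that removals under 4.4 would reach those numbers.

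**What to change.** **Sections 4.4 and 6.14.** Reword 4.4, and clarify in 6.14, that a deviation affecting interpretation is recorded and handled by PP-set exclusion at the Blind Data Review, and is not by itself a reason to end study follow-up. Leave all clinical reasons for stopping study drug unchanged.

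**Section 7.5.** Separate stopping study drug from leaving the study. Ask patients who stop study drug without withdrawing consent to keep the diary through Days 23-29 and hand it in at the planned Visit 3.

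**SAP 4.2.1.** Analyse those scores at least as a sensitivity analysis of the FAS primary endpoint. Making them the primary value would be an estimand choice that the sponsor should state openly. Tabulate investigator-initiated removals by arm, with reason and study day.

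**Cost.** Amendment wording, some off-treatment diary data, and slightly more site follow-up; the diary and Visit 3 already exist. Protocol 9.2 says all subjects had been recruited when Amendment 1 was written, and SAP 4.4 describes recruitment as so fast that an interim decision would have come after all screened patients had completed. Prospective diary collection may therefore reach few patients. The tabulation by arm does not depend on new collection and can be done in any case.

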4.5. Re-tests and re-screening

In case of obtaining uncertain of doubtful results of laboratory testing during the screening examination repeated testing (re-test) may be conducted once in agreement with the Sponsor or its authorized representative

The patients, who do not meet the inclusion/exclusion criteria due to manageable medical condition, can pass repeated Screening Visit after agreement from the Sponsor or his representative (re-screening). In this case, all screening procedures will be repeated, including the procedure for obtaining informed consent and assigning a new identification number.

Confidential Page 49 of 94

5. STUDY DRUG

5.1. Description of the investigated drugs

5.1.1. Fixed-dose combination Mebeverine + Simethicone

Study drug:	Mebeverine + Simethicone, film-coated tablets, 135 mg + 80 mg
Active substances:	Mebeverine hydrochloride and Simethicone
Pharmacological group	Analgesics and antispasmodics. ATC code: A03AX (or A03E)
Composition:	Active substances: Mebeverine hydrochloride 135.00 mg and Simethicone EP-100% 84.43 mg, corresponding to polydimethylsiloxane 80.00 mg
Daily dose and dosing regimen:	Orally 1 tablet 3 times a day before meal
Package description:	100 tablets (10 tablets in 10 Blisters PVC/PE/PVDC/Alu)
Storage conditions	In a light-protected place at a temperature not above 25°C. Keep out of the reach of children.
Manufacturer:	

5.1.2. Duspatalin ®

Study drug:	Duspatalin® coated tablets 135 mg
Active substance:	Mebeverine hydrochloride
Pharmacological group	Antispasmodics. ATC code: A03AA04
Composition:	Coated tablets
	Active substance: Mebeverine hydrochloride 135,0 mg
Daily dose and dosing regimen:	Orally 1 tablet 135 mg three times a day before meals
Package description:	10 tablets in a blister from PVC / aluminum foil. 1 or 5 blisters in a carton pack with package insert.
Storage conditions	Store at a temperature not higher than 30°C. Keep out of the reach of children.
Manufacturer:	Mylan Laboratories SAS, France

5.1.3. Espumisan®

Study drug:	Espumisan®, 40 mg capsules
Active substance:	Simethicone

Confidential Page 50 of 94

Pharmacological group	Carminative ATH code: A03AH13	
Composition:	40 mg capsules	
	Active substance: Simethicone 40,0 mg	
Daily dose and dosing regimen:	Orally 2 capsules 3 times a day after or before meal	
Package description:	25 capsules in a PVC / aluminum foil blister.	
	1, 2 and 4 blisters in a carton pack with Package Insert	
Storage conditions:	Store at a temperature not higher than 30°C. Keep out of the reach of children.	
Manufacturer:		

5.2. Administration of the study drug and randomization

At the visit 2 Week 0, Day 1, all eligible patients will be randomized into three equal groups (1:1:1):

- Mebeverine+Simethicone, 135 mg+80 mg, three times a day during 4 weeks
- Duspatalin® 135 mg three times a day during 4 weeks
- Espumisan®, 80 mg three times a day during 4 weeks

Patients will take the study drugs during 4 weeks: Mebeverine+Simethicone 1 tablet three times a day before meal, Duspatali® 1 tablet three times a day before meal, Espumisan ® 2 capsules 3 times a day after or before meal.

The last dose has to be taken at the evening before the Visit 3 (Week 4, Day 29).

The patients will register the study drug administration in the diary.

